7.0 Adverse Event Reporting

7.1 Definitions

7.1.1 Adverse Event Definition

Adverse event (AE) means any untoward medical occurrence in a patient or subject administered a donor convalescent plasma product; the untoward medical occurrence does not necessarily have a causal relationship with this treatment. An AE can therefore be any unfavorable and unintended sign (including an abnormal laboratory finding), symptom, or disease temporally associated with the use of the (investigational) product, whether or not it is related to the medicinal product. This includes any newly occurring event, or a previous condition that has increased in severity or frequency since the administration of study drug.

Only adverse events that are possibly, probably or definitely related to the infusion of convalescent plasma should be captured.

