7.1.2 Serious Adverse Event Reporting

The investigator will comply with all safety reporting regulations as set forth in the Code of Federal Regulations. The investigator being the sponsor of the study has the sole responsibility for reporting all serious adverse events to the Northside Hospital Institutional Review Board (the IRB of record), and if serious and either likely, possibly, probably, or definitely related to study drug to the FDA via Form3500A. The investigator will communicate the occurrence of serious adverse events to the IRB of record within 24 hours of becoming aware of the event.

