Clarification should be made between a serious AE (SAE) and an AE that is considered severe in intensity (Grade 3 or 4), because the terms serious and severe are NOT synonymous. The general term *severe* is often used to describe the intensity (severity) of a specific event; the event itself, however, may be of relatively minor medical significance (such as a Grade 3 headache). This is NOT the same as *serious*, which is based on patient/event outcome or action criteria described above and is usually associated with events that pose a threat to a patient's life or ability to function. A severe AE (Grade 3 or 4) does not necessarily need to be considered serious. For example, a white blood cell count of 1000/mm³ to less than 2000 is considered Grade 3 (severe) but may not be considered serious. Seriousness (not intensity) serves as a guide for defining regulatory reporting obligations.

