7.2 Procedures for Reporting Serious Adverse Events

Reporting will only be required for serious adverse events judged by the treating physician to be potentially related to the administration of COVID-19 convalescent plasma. This will include determination plasma related allergic reaction, urticarial eruption, adverse change in cardiopulmonary status and other organ injury. The NIH grading criteria will be utilized. Special consideration will include the development of TACO or TRALI blood transfusion associated reaction, and anaphylactic reaction temporally related to the infusion of the donor product transfusion.

Serious adverse events judged by the treating physician to be potentially related to the administration of COVID-19 convalescent plasma should be reported to the principal investigator.

All SAEs should be monitored until they are resolved or are clearly determined to be due to a patient's stable or chronic condition or intercurrent illness(es).

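### The serious adverse event rules contradict each other: section 7.1.2 owes every SAE to the IRB, but sections 7.1.1 and 7.2 capture and pass on only those judged related to plasma

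*Combined protocol and SAP*

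**What the plan says.** Three parts of section 7 of the combined protocol and SAP set the rules.

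- **Section 7.1.1 (capture).** The definition of an adverse event does not depend on cause. The closing sentence then narrows what is recorded: "Only adverse events that are possibly, probably or definitely related to the infusion of convalescent plasma should be captured". Serious events are not exempted.
- **Section 7.1.2 (duty to the IRB and the FDA).** The investigator, who is also the sponsor, "has the sole responsibility for reporting all serious adverse events to the" IRB of record, and must do so "within 24 hours of becoming aware of the event". Neither statement carries a relatedness condition. The condition appears only in the FDA clause, which covers events that are likely, possibly, probably, or "definitely related to study drug to the FDA via Form3500A".
- **Section 7.2 (procedure).** "Reporting will only be required for serious adverse events judged by the treating physician to be potentially related" to the plasma. SAEs judged "potentially related to the administration of COVID-19 convalescent plasma should be reported to the principal investigator". The section closes with a follow-up rule: "All SAEs should be monitored until they are resolved", or until they are clearly attributed to a stable or chronic condition or an intercurrent illness.

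Section 1.5 accepts that, in patients with infiltrates who need oxygen, it will be hard to tell whether an acute respiratory change was caused by the infusion.

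**The concern.** Staff who follow sections 7.1.1 and 7.2 to the letter leave the investigator unable to meet section 7.1.2. A physician who judges an SAE unrelated need not record it as an adverse event or tell the principal investigator. The 24-hour clock for the IRB starts only when the investigator becomes aware, so the report can be late or never made.

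The filter is one physician's judgement of cause, in a single-arm, unblinded trial that compares its results with historical rates. There is no concurrent group in which an excess of supposedly unrelated events could be seen, and the protocol itself says that attribution of respiratory change is difficult. If an SAE is not recorded as such, its timing relative to the infusion and the reason for the attribution are hard to check later. Section 8.7 allows closure for unacceptable risk in the investigator's opinion, and that opinion depends on this information.

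**Working it through.** **1. One event under each rule.** Take an SAE that the treating physician judges unrelated to plasma.

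| Section | Question | Answer for this event |
|---|---|---|
| 7.1.1 | Captured as an adverse event? | No |
| 7.1.2 | Owed to the IRB? | Yes, within 24 hours of awareness |
| 7.1.2 | Owed to the FDA? | No |
| 7.2 | Must the physician report it to the principal investigator? | No |
| 7.2, last sentence | Followed to resolution? | Arguably yes, but no route is given |

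The second row cannot be met reliably while the first and fourth stand. The treating physician and the principal investigator need not be the same person: section 8.6 refers to several study sites, and section 5.1.2 to delivery to outlying hospitals.

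**2. What stays visible.** Section 5.1.3 records hospital, ICU and ventilator days and daily diaries to Day 30 whatever the cause. Section 3.1.1 includes progression and multi-organ failure as endpoints. Section 5.3 keeps survival data after withdrawal of consent. Section 7.2 names TACO, TRALI, anaphylaxis and adverse cardiopulmonary change for reporting. These sources limit the gap but do not give a prompt report of an SAE judged unrelated.

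**3. Scale.** The documents state no SAE rate, so there is no figure to reproduce. Progressions to severe disease are the one kind of event whose number can be bounded. Let *s* be the unknown share that both meet an SAE criterion and are judged unrelated. The number on which the rules disagree is *s* × (expected enrolment × progression rate), summed over the two groups.

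*Projected rates, with the expected enrolment stated in section 6.1:*
- Group 3: 159 × 0.163 = 25.9
- Group 4: 152 × 0.075 = 11.4
- Sum: 37.3

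*Null rates.* Early stops are then rare, so expected enrolment was computed by exact binomial, with three looks and the section 6.3 rule (stop when the score upper limit with critical value 2.289 is below the null). The Group 3 maximum is taken as 3 × 76 = 228.

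| | Group 3 (null 25%) | Group 4 (null 14.8%) |
|---|---|---|
| Stop at look 1 if events ≤ | 10 of 76 | 3 of 73 |
| Stop at look 2 if events ≤ | 25 of 152 | 11 of 146 |
| P(stop) at look 1 | 0.0088 | 0.0035 |
| P(stop) at look 2 | 0.0055 | 0.0050 |
| Expected enrolment | 226.2 | 218.1 |
| Expected progressions | 226.2 × 0.25 = 56.6 | 218.1 × 0.148 = 32.3 |

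The sum is 88.8 (from unrounded values), close to the total at full enrolment: 228 × 0.25 + 219 × 0.148 = 57.0 + 32.4 = 89.4.

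*Cross-check.* The same calculation at the projected rates gives expected enrolment of 160.5 and 161.1 and 26.2 + 12.1 = 38.2 progressions (from unrounded values), close to 37.3.

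*Range.* As *s* runs from 0 to 1, the count runs from 0 to about 37 (projected) or 0 to about 89 (null). With *s* = 0.5 it is about 19 or 44. The upper ends are ceilings: the severe-disease thresholds in the Protocol Summary (respiratory rate, saturation, oxygenation index) are not SAE criteria in section 7.1.3, and some respiratory worsening may be judged potentially related and so be reported.

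**The case against.** The best defence is that the sections govern different steps: 7.1.2 the step from investigator to IRB, 7.2 the step from treating physician to investigator. On that reading the rules leave a gap but do not conflict. Awareness can come by any means, and much serious worsening is in the study data anyway. Section 7.1.2 also opens with a general commitment to federal safety-reporting rules, and the follow-up sentence in 7.2 contemplates SAEs that prove to have another cause.

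Part of this stands. Unrelated SAEs are not invisible, and a reader who infers that they have no path at all to the investigator goes too far. What is missing is a prompt path specific to SAEs. The two-step reading does not repair that, because the IRB duty depends on the step that 7.2 restricts and 7.1.1 still stops capture. The general commitment names no route. The follow-up sentence may cover only SAEs first judged potentially related; if it covers all SAEs, it asks for follow-up of events that 7.1.1 leaves unrecorded.

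A reader might also infer that safety endpoint 7 in section 3.1.1 contradicts the reporting rules, because it counts severe events where the rules speak of serious ones, and section 7.1.3 separates the two "because the terms serious and severe are NOT synonymous". The documents do not support that. Section 7.1.3 ties severe to Grade 3 or 4 and section 7.2 adopts NIH grading, so the endpoint can be read literally as Grade 3–4 events. Nor does any section promise an all-cause rate. This is a matter for clarification.

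**Conclusion.** The contradiction is established by the text of sections 7.1.1, 7.1.2 and 7.2 and does not depend on any rate. An SAE judged unrelated to plasma is owed to the IRB but is not captured as an adverse event and has no prompt SAE-specific route to the investigator. It should be corrected.

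Its size is uncertain. Among progressions, the rules disagree on 0 to about 37 events at the projected rates with the stated expected enrolment, or 0 to about 89 at the null rates. Where the true number falls depends on the share that are SAEs judged unrelated, which the documents do not give. It would be wrong to read 37 or 89 as a forecast of missed SAEs: these are ceilings, and progressions are recorded as the primary endpoint in any case. The gap matters most for SAEs outside the efficacy data, whose number cannot be estimated from the documents.

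**What to change.** Reconcile sections 7.1.1, 7.1.2 and 7.2. The resolution that keeps the duty already stated in 7.1.2 takes two edits:

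1. **Section 7.1.1, last sentence.** Record all SAEs from the start of transfusion to the end of participation (Day 30, or discharge if later) whatever the attribution, with relatedness as a separate field. Keep the related-only rule for non-serious events.
2. **Section 7.2.** Report all SAEs to the principal investigator. Relatedness decides only whether the FDA is also notified, as in 7.1.2.

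If the sponsor instead intends related-only reporting to the IRB, or an exemption for disease progression, section 7.1.2 must say so and the IRB must agree. Either way, one set of relatedness terms should be used, since the three sections now use three.

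As a separate clarification, item 7 of section 3.1.1 should state whether it means Grade 3–4 or serious events, and whether it counts plasma-related events only.

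**Cost.** Under the first resolution there are more SAE records and more physician-to-investigator reports: for progressions at most about 37 (projected rates) to 89 (null rates) over the whole trial, plus an unknown number of other SAEs. The IRB reports are no added burden, because 7.1.2 already requires them. Capture of non-serious events is unchanged, and hospital, ICU and ventilator days are already recorded under section 5.1.3.

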7.1.2 Serious Adverse Event Reporting

The investigator will comply with all safety reporting regulations as set forth in the Code of Federal Regulations. The investigator being the sponsor of the study has the sole responsibility for reporting all serious adverse events to the Northside Hospital Institutional Review Board (the IRB of record), and if serious and either likely, possibly, probably, or definitely related to study drug to the FDA via Form3500A. The investigator will communicate the occurrence of serious adverse events to the IRB of record within 24 hours of becoming aware of the event.

7.1.3 Serious Adverse Event Definition

Serious AE (SAE) means any untoward medical occurrence that at any dose:

- Results in death.
- Is **life-threatening** (refers to an AE in which the patient was at risk of death at the time of the event. It does not refer to an event which hypothetically might have caused death if it were more severe).

- Requires inpatient **hospitalization or prolongation of an existing hospitalization** (see clarification in the paragraph below on planned hospitalizations).
- Results in persistent or significant disability or incapacity. (Disability is defined as a substantial disruption of a person's ability to conduct normal life functions).
- Is a congenital anomaly/birth defect.
- Is a **medically important event**. This refers to an AE that may not result in death, be immediately life threatening, or require hospitalization, but may be considered serious when, based on appropriate medical judgment, may jeopardize the patient, require medical or surgical intervention to prevent 1 of the outcomes listed above, or involves suspected transmission via a medicinal product of an infectious agent. Examples of such medical events include allergic bronchospasm requiring intensive treatment in an emergency room or at home, blood dyscrasias or convulsions that do not result in inpatient hospitalization, or the development of drug dependency or drug abuse; any organism, virus, or infectious particle (e.g., prion protein transmitting Transmissible Spongiform Encephalopathy), pathogenic or nonpathogenic, is considered an infectious agent.
- Results in a development of drug dependency or drug abuse
- Is a serious adverse drug experience

Clarification should be made between a serious AE (SAE) and an AE that is considered severe in intensity (Grade 3 or 4), because the terms serious and severe are NOT synonymous. The general term *severe* is often used to describe the intensity (severity) of a specific event; the event itself, however, may be of relatively minor medical significance (such as a Grade 3 headache). This is NOT the same as *serious*, which is based on patient/event outcome or action criteria described above and is usually associated with events that pose a threat to a patient's life or ability to function. A severe AE (Grade 3 or 4) does not necessarily need to be considered serious. For example, a white blood cell count of 1000/mm³ to less than 2000 is considered Grade 3 (severe) but may not be considered serious. Seriousness (not intensity) serves as a guide for defining regulatory reporting obligations.

7.2 Procedures for Reporting Serious Adverse Events

Reporting will only be required for serious adverse events judged by the treating physician to be potentially related to the administration of COVID-19 convalescent plasma. This will include determination plasma related allergic reaction, urticarial eruption, adverse change in cardiopulmonary status and other organ injury. The NIH grading criteria will be utilized. Special consideration will include the development of TACO or TRALI blood transfusion associated reaction, and anaphylactic reaction temporally related to the infusion of the donor product transfusion.

Serious adverse events judged by the treating physician to be potentially related to the administration of COVID-19 convalescent plasma should be reported to the principal investigator.

All SAEs should be monitored until they are resolved or are clearly determined to be due to a patient's stable or chronic condition or intercurrent illness(es).

8.0 ADMINISTRATIVE REQUIREMENTS

8.1 Good Clinical Practice

The study will be conducted in accordance with the International Conference on Harmonization (ICH) for Good Clinical Practice (GCP) and the appropriate regulatory requirement(s). The investigator will be thoroughly familiar with the appropriate use of the study drug as described in the protocol and Investigator's Brochure. Essential clinical documents will be maintained to demonstrate the validity of the study and the integrity of the data collected. Master files should

be established at the beginning of the study, maintained for the duration of the study and retained according to the appropriate regulations.

8.2 Ethical Considerations

The study will be conducted in accordance with applicable regulatory requirement(s) and will adhere to GCP standards. The IRB/IEC will review all appropriate study documentation in order to safeguard the rights, safety and well-being of the patients. The study will be conducted only at sites where IRB/IEC approval has been obtained. The protocol, informed consent form, advertisements (if applicable), written information given to the patients (including diary cards), safety updates, annual progress reports, and any revisions to these documents will be provided to the IRB/IEC by the investigator.

8.3 Patient Information and Informed Consent

After the study has been fully explained, written informed consent will be obtained from either the patient or his/her guardian or legal representative before study participation using the most current IRB approved consent form. The method of obtaining and documenting the informed consent and the contents of the consent must comply with the ICH-GCP and all applicable regulatory requirements. The participant must be given a copy of the signed and dated consent document. The original signed copy of the consent document must be retained in the medical record or research file.

8.4 Patient Confidentiality

In order to maintain patient privacy, all data capture records, drug accountability records, study reports and communications will identify the assigned patient number. The patient's confidentiality will be maintained and will not be made publicly available to the extent permitted by the applicable laws and regulations.

8.5 Investigator Compliance

The investigator will conduct the study in compliance with the protocol given approval/favorable opinion by the IRB/IEC and the appropriate regulatory authority(ies). The IRB/IEC may provide, if applicable regulatory authority(ies) permit, expedited review and approval/favorable opinion for minor change(s) in ongoing studies that have the approval /favorable opinion of the IRB/IEC. Any departures from the protocol must be fully documented in the source documents.

8.6 Investigator and Site Responsibility for COVID-19 Donor Convalescent Plasma Accountability

Accountability for the administration of convalescent plasma at all study sites is the responsibility of the principal investigator. The investigator will ensure that the convalescent plasma product(s) is used only in accordance with this protocol. Accountability records will include dates, quantities, lot numbers, expiration dates (if applicable), and patient numbers.

8.7 Closure of the Study

This study may be prematurely terminated, if in the opinion of the investigator there is sufficient reasonable cause.

Circumstances that may warrant termination include, but are not limited to:

- Determination of unexpected, significant, or unacceptable risk to patients
- Failure to enter patients at an acceptable rate
- Insufficient adherence to protocol requirements
- Insufficient, incomplete and/or unevaluable data
- Determination of efficacy based on interim analysis

8.8 Record Retention

The investigator will maintain all study records according to the ICH-GCP and applicable regulatory requirement(s).

8.9 COVID-19 Convalescent Plasma Products

Convalescent Plasma products will be provided by donor blood centers in accordance with FDA regulations and guidance. This will be transported to hospital blood bank for storage and subsequent distribution to the study patient, per FDA regulator guidelines for transportation, storage and distribution and transfusion of blood products.

